## 6.6.3 Definition of Dose-limiting Toxicity

The DLTs will be evaluated during Part A Dose Escalation. The DLT evaluation period will be 28 days from the first dose of sabestomig on Cycle 1 Day 1. Participants who do not remain in the study for the entire duration of the DLT evaluation period, for reasons other than DLT, will be considered non-evaluable for DLT evaluation and will be replaced with another participant at the same dose level if needed to ensure a minimum of CCI evaluable participants in the ATD and mTPI-2 cohorts, respectively.

A DLT will be defined during Part A Dose Escalation as any  $\geq$  Grade 3 AE as per NCI CTCAE version 5 unless unequivocally due to underlying malignancy or an extraneous cause. The modifications and exceptions to this are detailed below.

The following conditions will be considered as DLTs:

- Any death not clearly due to the underlying disease or extraneous causes.
- Grade 4 imAE.
- Any  $\geq$  Grade 3 non-infectious pneumonitis irrespective of duration.
- Any  $\geq$  Grade 3 non-infectious colitis irrespective of duration.
- Liver transaminase elevation:
  - Isolated liver transaminase elevation > 5 x but  $\le 10$  x ULN that does not downgrade to AST/ALT  $\le 3$  x ULN or less within 7 days after onset with optimal medical management including systemic corticosteroids.
  - Transaminase elevation > 10 x ULN regardless of duration or reversibility.
  - Isolated TBL elevation > 3 x ULN that does not downgrade to ≤ 1.5 x ULN within 7 days after onset with optimal medical management (for participants with Gilbert's syndrome: TBL > 3 x ULN and doubling of direct bilirubin that does not downgrade to baseline value within 7 days).
  - Any increase in AST/ALT > 3 x ULN and concurrent increase in TBL  $\ge$  2 x ULN, regardless or duration or reversibility, where no other reason, other than the investigational product(s), can be found to explain the combination of increases (for participants with Gilbert's syndrome: TBL > 3 x ULN and doubling of direct bilirubin that does not downgrade to baseline value within 7 days).
- Any Grade 3 imAE, including rash, pruritus, or diarrhea (NOTE: this excludes colitis or pneumonitis, as these AEs are already defined above), that does not downgrade to Grade 2 or less within 7 days after onset of the event despite maximal supportive care including systemic corticosteroids.

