#### 9.4.3 Safety Analyses

Safety and tolerability will be assessed in terms of DLTs, AEs/SAEs, imAEs, vital signs, clinical chemistry/hematology parameters, and clinically significant abnormalities in ECGs. These variables will be collected for all participants where applicable. All safety analyses will be performed on the safety analysis set. Additional subgroup analysis of safety may be performed, as specified in the SAP.

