#### 9.4.3.1 Maximum Tolerated Dose Evaluation

The MTD evaluation will be based on the DLT-evaluable population. After each escalation stage is completed, final DLT rates at each dose level will be estimated by isotonic regression (Ji et al, 2010). The weighted least squares regression model will assume monotonic non-decreasing DLT rates with increasing dose, and use the empirical (observed) DLT rates at each dose level as responses and dose level sample sizes as weights, along with the pool adjacent violators algorithm to estimate the DLT rate at each dose level using available software such as EAST® and R. Given the DLT estimates for each dose level, the MTD will be selected from all tried dose levels that have not been previously declared to be unsafe (Probability [DLT > 30% data]  $\geq$  80%) with a DU decision according to the mTPI-2 decision table. With this constraint, the MTD will be determined as the dose level with the DLT estimate closest to the target toxicity level of 30%.

In the case of dose levels with estimated toxicity of equal distance (tied dose levels) from the target toxicity of 30%, the following approach will be used (Ji et al, 2010): among all tied dose levels, the highest dose level with target toxicity  $\leq$  30% will be selected, unless all tied dose levels have estimated toxicity > 30%, in which case the lowest dose level will be selected.

The number and percentage of participants with a DLT will also be presented by dose level.

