3.2 Analysis Populations

All participants who receive any amount of study intervention will be included in the Safety analysis set. For the safety and PK analyses, participants will be classified according to dose level they actually received. For all efficacy analyses, and for baseline and demography, participants will be classified according to the dose they were assigned to (ie, the planned dose level).

The analysis sets will be summarized and any exclusions from analysis sets will be presented in data listings that will include:

- participants excluded from the analysis set and
- data excluded from any analysis (e.g.: data censored at time of intra-participant dose escalation).

The following populations are defined:

Table 1 Populations for Analyses

Population/Analysis set	Description	Endpoint/Output
Enrolled	All participants who sign the Informed Consent Form (ICF), or whose legally authorized representative sign the Informed Consent Form.	Disposition
Full/Safety	All participants who receive any amount of study intervention.	Exposure Safety Baseline and demography PK concentrations and parameters Listings PFS OS
ITT	Participants assigned to study intervention.	Sensitivity analyses
Interim safety	All participants who received the first dose at least CCI to data cut-off.	Safety at interim
DLT-evaluable	Participants enrolled in the dose escalation phase who have received sabestomig and completed the DLT evaluation period (defined as 28 days after the start of study intervention) or who experienced any DLT.	DLT
Response-evaluable	All dosed participants who had measurable disease at baseline.	ORR CRR BOR Duration of response Duration of complete response
Interim response- evaluable	All dosed participants who had measurable disease at baseline and received first dose at CCI prior to data cut-off.	Efficacy at interim
PK	All participants who received at least 1 dose of study intervention with at least 1 reportable concentration.	PK concentrations PK parameters
Pharmacodynamics	All participants who received at least 1 dose of study intervention with at least 1 reportable pharmacodynamic measurement.	Pharmacodynamic endpoints
Immunogenicity	All participants who received at least 1 dose of study intervention with at least 1 reportable immunogenicity measurement.	Immunogenicity endpoints

-ed 30

		•
Population/Analysis set	Description	Endpoint/Output

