4.1.8.2 Presentation

The number and percentage of participants who took prior and concomitant medications or had concomitant procedures will be summarized by ATC classification codes and the generic term coded by WHO Drug Global B3 Sep 2021 or later for the FAS by dose level/cohort.

All prior, concomitant and post study intervention medication data will be listed.

Missing coding terms will be listed and summarized as "Not coded".

In addition, post study drug - anti-cancer therapies for cHL post study drugs - HSCT and post study drugs - radiotherapies will be listed as well as summarized (number and percentage of subjects).

4.2 **Endpoint Analyses**

This section covers details related to the endpoint analyses such as primary, secondary, other endpoints including sensitivity and supportive analyses.

Table 2 Endpoint Analyses					
Statistical category	Endpoint	Population	Population level summary (analysis)	Details in section	
Part A Dose Escal	ation				
Objective 1: To a	ssess the safety and tolerab	ility of sabestomi	g in participants with	r/r cHL	
Primary	AEs, imAEs, SAEs, AEs leading to discontinuation of sabestomig, Laboratory data changes, vital signs changes and ECG changes	Safety analysis set	Descriptive statistics on safety endpoints	4.5.2 (AEs) 4.5.4 and 4.5.5 (laboratory data) 4.5.6 (vital signs) 4.5.7 (ECG)	
Primary	Incidence of dose- limiting toxicities	Safety analysis set	Dose-limiting toxicities	4.5.10.1 DLT	
Part B Dose Expa Objective 2: To a	nsion (all) ssess the safety and tolerab	ility of sabestomi	g in participants with	r/r cHL	
Primary	AEs, imAEs, SAEs, AEs leading to discontinuation of sabestomig Laboratory data changes, vital signs changes and ECG changes	Safety analysis set	Descriptive statistics on safety endpoints	4.5.2 (AEs) 4.5.4 and 4.5.5 (laboratory data) 4.5.6 (vital signs) 4.5.7 (ECG)	
Part B Dose Expa Objective 3: To a (anti-PD-1/PD-L1	ssess the preliminary antit	ımor activity of s	abestomig in participa	nnts with r/r cHL	
Primary	Objective Response Rate [a]	Response evaluable set	ORR and 95% CI	4.2.2	
Objective 4: To a	Part B Dose Expansion (B2) Objective 4: To assess the preliminary antitumor activity of sabestomig in participants with r/r cHL (anti-PD-1/PD-L1 naïve)				
Primary	Complete Response Rate [a]	Response evaluable set	CR rate and 95% CI	4.2.3	
Part A Dose Escalation Objective 5: To assess the preliminary antitumor activity of sabestomig in participants with r/r cHL					

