4.5.10.2 Presentations

The MTD evaluation will be based on the DLT evaluable population. The number and percentage of participants with DLT during the dose escalation phase will be presented by treatment groups.

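### SAP Table 2 puts the Part A primary endpoint of DLT incidence on the Safety analysis set, while SAP Table 1 and Protocol Table 21 put DLTs on the DLT-evaluable set

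*SAP*

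**What the plan says.** In SAP Section 4.2, Table 2 is the map from endpoint to population. Under Objective 1 for Part A, its second primary row is "Incidence of dose- limiting toxicities". The population cell of that row reads Safety analysis set, and the row sends the reader to Section 4.5.10.1.

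SAP Section 3.2 defines that set broadly: "All participants who receive any amount of study intervention will be included in the Safety analysis set". Table 1 in the same section has a separate DLT-evaluable row, whose endpoint column reads DLT. It covers "Participants enrolled in the dose escalation phase who have received sabestomig and completed the DLT evaluation period", plus anyone who had a DLT. Protocol Table 21 gives the same definition and the same endpoint assignment.

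Protocol 6.6.3 explains how the two sets come apart. A participant who leaves the 28-day period early for a reason other than a DLT "will be considered non-evaluable for DLT evaluation and will be replaced with another participant at the same dose level", where this is needed to reach the required minimum.

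For the MTD the two documents agree. Protocol 9.4.3.1 states "The MTD evaluation will be based on the DLT-evaluable population", and SAP 4.5.10.2 states "The MTD evaluation will be based on the DLT evaluable population". The next sentence of SAP 4.5.10.2 produces the DLT table and names no denominator: "The number and percentage of participants with DLT during the dose escalation phase will be presented by treatment groups".

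A general rule points the other way. Protocol 9.4.3 lists DLTs among the safety assessments and then says "All safety analyses will be performed on the safety analysis set". SAP 4.5 likewise provides its tables on the safety analysis set. SAP Section 2 records no change to the planned analyses.

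**The concern.** One primary endpoint has two stated populations, and they can differ in membership. A programmer who follows Table 2 and the opening of SAP 4.5 will divide the DLT count by everyone dosed. A programmer who follows Table 1 will divide by the evaluable participants.

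The first choice counts people who were not observed for the whole DLT period as if they had completed it without a DLT. In a dose-finding part with cohorts of 3 to 12 (SAP 3.3.7.1), one such person moves the percentage visibly, and always downwards. The report could then show a primary DLT incidence at a dose level that does not match the DLT rate used for the MTD at the same level.

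**Working it through.** **Inputs.** Safety set and DLT-evaluable set: SAP Table 1. Non-evaluable participants: Protocol 6.6.3 and 6.6.6. Target DLT rate 30% and equivalence interval 25% to 33%: Protocol 6.6.1.2. Cohort size 3 to 12: SAP 3.3.7.1. The number of dosed but non-evaluable participants per dose level, k, is not given; I assume 0 to 2.

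**The plan's own figures.** The documents state no expected DLT rate, so the figures to reproduce are the decisions in Protocol Table 15. I used a Beta(1+x, 1+n−x) posterior, intervals of width 0.33 − 0.25 = 0.08, and DU when Pr(rate > 30%) is at least 80%. Every cell for 0 to 4 DLTs and n = 1 to 12 matches once footnotes a, b, c and e are applied. For example:

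- 2 DLTs in 3: Pr = 0.916, so DU.
- 2 DLTs in 6: Pr = 0.647, so not DU; the interval rule gives D.
- 3 DLTs in 7: Pr = 0.806, so DU.

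The columns of that table count evaluable participants.

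**Numerator.** Let x be the number of participants in the escalation phase with a DLT at a dose level. By the definition in SAP Table 1, each of them is DLT-evaluable. Each was also dosed, so each is in the Safety set. The numerator is x in both sets.

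**Denominator.** Let n be the number evaluable. The Safety set has n + k.

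- DLT-evaluable rate = x / n
- Safety-set rate = x / (n + k)
- Ratio of the second to the first = n / (n + k), which is 1 when k = 0 and below 1 otherwise

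**Results.**

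| DLTs / evaluable | k = 0 | k = 1 | k = 2 |
|---|---|---|---|
| 1/3 | 1/3 = 33.3% | 1/4 = 25.0% | 1/5 = 20.0% |
| 2/6 | 2/6 = 33.3% | 2/7 = 28.6% | 2/8 = 25.0% |
| 3/9 | 3/9 = 33.3% | 3/10 = 30.0% | 3/11 = 27.3% |

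With one non-evaluable participant, the relative understatement is 1/4 = 25.0% at n = 3, 1/7 = 14.3% at n = 6 and 1/10 = 10.0% at n = 9. Each row starts just above the 33% limit of the equivalence interval. With one such participant, the reported figure falls to the interval's lower limit (first row) or inside it (the other two).

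**Does another section settle the denominator?** Table 2 refers to SAP 4.5.10.1, which describes the isotonic estimation for the MTD and names no population for incidence. The first sentence of SAP 4.5.10.2 covers the MTD only. The second, which yields the count and percentage, is silent. The only passages that assign the DLT endpoint itself to a population are Table 1 and Table 21 on one side and Table 2 on the other.

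**The case against.** The strongest reply is that Table 2 follows the protocol. Protocol 9.4.3 and the synopsis put all safety analyses on the safety analysis set and count DLTs among them. SAP 3.2 also lets summaries be shown on more than one population. That is the likely origin of the entry, and it means the ambiguity began in the protocol; it would be unfair to say the SAP departs from a uniform rule. It does not justify the entry. Both population tables give DLTs a set of their own, and a rule written for one endpoint should govern over a general one.

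A second reply is that nothing is diluted if every dosed participant is evaluable, and that SAP 3.3.1 only lists dose levels with a single participant, so no percentage is planned for the single-participant titration cohorts. Both statements are right. The effect is conditional and concerns the mTPI-2 cohorts.

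A third is that Protocol 6.6.3 allows an event outside the DLT period to be declared a DLT, so a participant who left early might still count. Under Table 1 that person would then be DLT-evaluable, because the definition admits anyone with a DLT. The numerators stay equal.

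A reader might infer that the Table 2 entry could change an escalation decision, since Table 15 shows D at 2/6 and S at 2/8. The documents do not support that. Table 15 is read by evaluable participants, Protocol 6.6.6 restricts escalation decisions to them, and both documents base the MTD on them. Six evaluable and two non-evaluable participants are read in column 6, never column 8.

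**Conclusion.** The contradiction is real and the plan is wrong as written for this endpoint. Following Table 2 gives a DLT incidence equal to or lower than the one the population tables call for. The two agree when all dosed participants are evaluable. With one or two non-evaluable participants at a dose level, a true 33.3% would be reported as 25.0% or 20.0% on three evaluable participants, and as 28.6% or 25.0% on six. The range of 0 to 2 is my assumption.

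The consequence is limited to a descriptive percentage, for one of several Part A primary endpoints, in a study with no formal hypotheses. The documents do not support reading this as a threat to the escalation rules or the MTD, or as a bias certain to occur. It deserves correction because the endpoint is primary, the error has only one direction, and no other sentence in the SAP names the denominator for the percentage.

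**What to change.** - In SAP Table 2, change the population for DLT incidence to the DLT-evaluable set.
- In the second sentence of SAP 4.5.10.2, state that the percentage uses the DLT-evaluable set at each dose level.
- In SAP 4.5, except DLT rates from the statement that tables use the safety analysis set. The same exception belongs in Protocol 9.4.3 at its next revision.
- Keep a listing of DLTs on the Safety set if wanted. Showing the number dosed but non-evaluable per dose level beside the rate would let readers reconcile the two sets.
- In the same edit, correct the reference in SAP 4.5.10.1: it cites Protocol 9.4.3.1 for the definition of a DLT, which is in Protocol 6.6.3.

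The cost is one table cell and a few words in two SAP sections. No data collection, sample size or decision rule changes.

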4.2.2 Primary Endpoint: ORR

The primary efficacy endpoint for Part B Dose Expansion (B1) is ORR assessed by BICR based on modified Lugano criteria for lymphoma. ORR is a secondary endpoint for Part A Dose Escalation assessed by Investigator based on modified Lugano criteria and RECIL criteria.

4.2.2.1 Definition and Derivations

Objective Response (OR) is defined as a Best Overall Response (BOR) of CR or PR that occurs prior to the initiation of subsequent anticancer treatment and prior to progression. Objective Response Rate (ORR) is defined as the percentage of participants with objective response.

Data obtained from first dose until progression, or last evaluable assessment in the absence of progression, will be included in the assessment of ORR, regardless of whether the participant withdraws from therapy. Participants who discontinue treatment without a response, receive subsequent anti-lymphoma therapy and then respond will not be included as responders in the ORR (ie, the visit contributing to a response must be prior to subsequent therapy for the participant to be considered as a responder).

The ORR will be based on the BICR assessment, using modified Lugano criteria for lymphoma including data of all scans for Part B, regardless of whether it was scheduled or not.

ORR for Part A will be defined similarly but taking Investigator responses and based on modified Lugano criteria and RECIL criteria. Data will be recorded in the eCRF.

Best overall response

Best Overall Response (BoR) will be determined using disease assessments at different evaluation time points from the date of the first dose of study treatment until documented disease progression or start of any further anti-cancer therapy, whichever is earlier. Clinical deterioration will not be considered as documented disease progression. Categories of BOR will be based on modified Lugano criteria using the following response criteria: CR, PR, stable disease [SD], progressive disease [PD], and not evaluable [NE], and RECIL criteria using the following criteria: CR, PR, minor response [MR], SD, PD, and NE.

BoR will be calculated based on Investigator assessed data for part A efficacy analysis based on RECIL criteria, and based on BICR assessed data for part B analysis. The images of the participants dosed at RP2D in part A will undergo a retrospective assessment by BICR whose result will be combined with other BICR-based part B data for Part B analysis.

For participants without documented progression or subsequent therapy, all available response designations will contribute to the BOR determination. For purpose of analysis, if a participant receives one dose and discontinues the study without assessment or receives subsequent therapy prior to assessment, this participant will be counted in the denominator (as non-responder).

4.2.2.2 Primary Analysis of Primary Endpoint: ORR

Summaries will be produced that present the number and percentage of participants with a response (CR/PR) based upon the number of participants in the response-evaluable analysis set. ORR will be presented with 95% CI based on exact binomial proportions.

BoR will be summarized by number of participants and percentage for each category (CR, PR, MR [for RECIL criteria], SD, PD, and NE). No formal statistical analyses are planned for BoR.

4.2.2.3 Sensitivity Analysis of ORR Endpoint

As sensitivity analysis, if the number of participants in FAS is different from that in Response Evaluable Set, a summary of will be used in this analysis. For the computation of ORR, participants with will be included in the FAS and will be considered non-responders.

4.2.2.4 Supportive Secondary Analysis of ORR Endpoint

A supportive secondary analysis of ORR for Part B will be presented using Investigator assessments and based on modified Lugano criteria and RECIL. Data recorded in eCRF will be used for this analysis.

- ed. 3.0

4.2.2.5 Supportive Secondary Analysis: Change in Target Lesion Tumor Size

Change in target lesion tumor size will be presented as supportive secondary analysis for Part A and Part B.

4.2.2.5.1 Definition and Derivations: Change in Target Lesion Tumor Size

Target lesions are measurable tumor lesions. Baseline is defined to be the last evaluable assessment prior to starting treatment.

Target lesion tumor size for lymph nodes and extra-lymphatic sites at any timepoint is defined as the sum of the product of the perpendicular diameters for multiple lesions. When a lesion is too small to measure, 5 mm x 5 mm will be assigned as the product of the perpendicular diameters.

The percentage change in target lesion size at each timepoint for which data are available will be obtained for each participant, taking the difference between the sum of the perpendicular diameters (SPD) of target lesions at each timepoint and the sum of the product of the perpendicular diameters of target lesions at baseline multiplied by 100 (ie, [timepoint – baseline]/baseline x 100).

4.2.2.5.2 Analysis of Supportive Data: Change in Target Lesion Tumor Size

Only participants included in the response-evaluable analysis set will be included in summaries of change in tumor size.

The target lesion tumor size (SPD of lymph node) and percentage change from baseline in target lesion tumor size may be summarized using descriptive statistics and presented at each timepoint.

Additionally, 'spider' plots of percentage change from baseline in target lesion size by participants will be presented. A graphical summary of the best percentage change in target lesion tumor size will be presented in a vertical bar chart with each participant's percentage change from baseline to nadir displayed as a vertical bar, with colour coding that indicates best response obtained ("waterfall" plot).

4.2.2.6 Subgroup Analyses

The following subgroup analysis may be performed for ORR (primary efficacy variable):

 Participants who are brentuximab naïve versus participants who are brentuximab exposed. Exposure to brentuximab will be identified from the participant's concomitant medications record.

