#### **Current or Prior Therapy**

- 17 Current or prior use of immunosuppressive medication within 14 days prior to the first dose of study intervention. The following are exceptions to this criterion:
  - (a) Intranasal, inhaled, topical steroids, or local steroid injections (eg, intra-articular injection).
  - (b) Systemic corticosteroids at physiological doses not to exceed 10 mg/day of prednisone or its equivalent.
  - (c) Steroids as premedication for hypersensitivity reactions (eg, CT scan premedication).
- 18 Any concurrent chemotherapy, radiotherapy, investigational, biologic, or hormonal therapy for cancer treatment.
  - (a) Concurrent use of hormonal therapy for noncancer-related conditions (eg, insulin for diabetes and hormone replacement therapy) is acceptable.
  - (b) A washout period of at least 28 days after the last chemotherapy, radiotherapy, investigational, biologic, or hormonal therapy for cancer treatment must be followed before the administration of sabestomig.
- 19 Receipt of live attenuated vaccine within 30 days prior to the first dose of study intervention.

**NOTE:** Participants should not receive live vaccine while receiving study intervention and up to 30 days after the last dose of study intervention.

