## 6.5 Concomitant Therapy

Any medication or vaccine or supplement (including over-the-counter or prescription medicines, vitamins, and/or herbal supplements) that the participant is receiving at the time of enrollment or receives during the study must be recorded along with:

- Reason for use.
- Dates of administration including start and end dates.
- Dosage information including dose, frequency, and route of administration.

The Study Physician should be contacted if there are any questions regarding concomitant or prior therapy.

Use of concomitant medications including over-the-counter medications, herbal supplements, vitamins, etc., from time of screening until the final study visit is not permitted without first consulting with the Investigator or delegate.

Prohibited concomitant medications are detailed in Table 12 and permitted concomitant medications are detailed in Table 13.

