## 8.2.1 Medical History

A medical and surgical history, including but not limited to, substance usage (eg, smoking and alcohol consumption history), comorbid conditions, tumor diagnosis and histology, PD-L1 status, EBV status, and prior cancer therapies, will be obtained at screening. Based on findings from medical history, ongoing current conditions will be given a baseline grade (NCI CTCAE v5.0). Increases in severity of pre-existing conditions during the study will be considered AEs, with resolution occurring when the grade returns to the baseline grade or below.

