3.3.6 Missing Dates

When partial dates exist in the data there are some general conventions to be applied when the month or day are missing. These are described in the PHUSE guidance on partial dates, which are outlined below:

If the whole date is missing, it is more difficult to follow a general principle and these are reviewed within the study and decided on how to be handled. General guidance for completely missing dates are provided below, but the guidance is assessed as necessary within the study.

Generally, the imputation of dates is used to decide if an observation is treatment emergent for adverse events (AEs) or concomitant medications. The imputed dates should not be used to calculate durations, where the results would be less accurate.

The following are the guidelines used when partial dates are detected in the study:

- For missing diagnostic dates (eg,: disease diagnosis), if day and/or month are missing use
 01 and/or Jan. If year is missing, put the complete date to missing.
- For missing AE and concomitant medication start dates, the following is applied:
 - a. Missing day impute the 1st of the month unless month is the same as month of the first dose of study drug then impute first dose date.
 - b. Missing day and month impute 1st January unless year is the same as first dose date then impute first dose date.

- c. Completely missing impute first dose date unless the end date suggests it could have started prior to this in which case impute the 1st January of the same year as the end date.
- Imputed start date should be no later than the end date.
- For missing AE and concomitant medication end dates, the following is applied:
 - a. Missing day impute the last day of the month unless both the month and the year are the same as the last dose date or the analysis data cut-off date then impute the last dose date or the analysis data cut-off date.
 - b. Missing day and month impute 31st December unless the year is the same as the last dose date or the analysis data cut-off date then impute the last dose date or the analysis data cut-off date.

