 - c. Completely Missing need to look at whether the AE/medication is still ongoing before imputing a date and also when it started in relation to study drug. If the ongoing flag is missing then assume that AE is still present / medication is still being taken (ie, do not impute a date). If the AE/medication has stopped and start date is prior to first dose date then impute first dose date. Or if it started on or after first dose date then impute to the last dose of study drug date + 1.
- Flags are retained in the database indicating where any programmatic imputation has been applied, and in such cases for AEs and concomitant medications, any durations would not be calculated.
- If a participant is known to have died where only a partial death date is available then the
 date of death is imputed as the latest of the last date known to be alive +1 from the
 database and the death date, using the available information provided and applying the
 following:
 - For Missing day only using the 1st of the month.
 - For Missing day and Month using the 1st of January.

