4.1.8 Prior and Concomitant Medications/Procedures

4.1.8.1 Definitions and Derivations

For the purpose of inclusion in prior and/or concomitant medication, procedures or therapy summaries, incomplete medication or radiotherapy start and stop dates are imputed as detailed in Section 3.3.6.

Prior medications, concomitant and post-treatment medications or procedures are defined based on imputed start and stop dates as follows:

- Prior medications/procedures are those taken prior to study treatment with a stop date prior to the first dose of study treatment.
- Concomitant medications/procedures are those with a stop date or ongoing on or after
 the first dose date of study treatment, and must have started prior to or during treatment so
 there is at least one day in common with the study treatment.
- Post-treatment medications/procedures are those with a start date after the last dose date
 of study treatment plus 90 days.

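### The optional brentuximab subgroup takes exposure from the concomitant-medication record, so participants with a complete pre-study stop date would be labelled naive

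*SAP*

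**What the plan says.** SAP 4.2.2.6 allows one ORR subgroup analysis, brentuximab naive versus brentuximab exposed, and names the data source: "Exposure to brentuximab will be identified from the participant's concomitant medications record". SAP 4.2.3.5 allows the same split for CRR and names no source.

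SAP 4.1.8.1 defines the medication classes by imputed dates:

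- Prior: "Prior medications/procedures are those taken prior to study treatment with a stop date prior to the first dose of study treatment".
- Concomitant: "Concomitant medications/procedures are those with a stop date or ongoing on or after" the date of first dose, with at least one day shared with study treatment.

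SAP 3.3.6 gives the stop-date imputation. If day and month are missing: "impute 31st December unless the year is the same as the last dose date or the analysis data cut-off date", in which case that date is used. If the date is wholly missing: "If the AE/medication has stopped and start date is prior to first dose date then impute first dose date".

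The protocol handles earlier cancer treatment apart from concomitant therapy. Section 6.5 covers any medication "that the participant is receiving at the time of enrollment or receives during the study must be recorded along with" its reason, dates and dosage. Section 8.2.1, Medical History, covers past treatment: "PD-L1 status, EBV status, and prior cancer therapies, will be obtained at screening". Exclusion 18 bars concurrent cancer therapy, and 18(b) adds: "A washout period of at least 28 days after the last chemotherapy, radiotherapy, investigational, biologic, or hormonal therapy for cancer treatment must be followed". SAP 4.1.7.2 summarizes prior anti-cancer therapy for cHL by ATC class and generic drug name.

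**The concern.** Brentuximab exposure is meant to describe treatment history before sabestomig. The named source covers a different period. An eligible participant finished any earlier brentuximab at least 28 days before first dose, so with complete dates that course is prior under the SAP's own definition. With only two levels and that one source, the participant falls into the naive group.

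Membership of the exposed group would then depend mostly on how incomplete the stop date is. The naive group would mix treated and untreated participants, which pulls any real difference towards zero. The exposed group could be very small or empty.

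This is the only efficacy subgroup the SAP specifies, and it appears under both primary efficacy endpoints. Because the CRR section names no source, the two endpoints could also be split differently.

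**Working it through.** The plan gives no figure to reproduce, so the check applies the SAP's rules to dates.

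**Rule applied.** Impute the stop date by SAP 3.3.6. If the result is before first dose, the drug is prior. If it is on or after first dose and the drug overlaps treatment, it is concomitant (SAP 4.1.8.1).

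**Worked dates** (assumed: first dose 15 June 2023, last dose 1 December 2023, cut-off 1 September 2024, brentuximab started January 2021):

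| Recorded stop | Imputed stop | Class |
|---|---|---|
| 1 March 2022 | none needed | prior |
| 18 May 2023 (28 days before first dose) | none needed | prior |
| March 2022, day missing | 31 March 2022 | prior |
| 2022 only | 31 December 2022 | prior |
| 2023 only | 1 December 2023 | concomitant |
| Wholly missing, drug stopped | 15 June 2023 | concomitant |

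**Complete dates.** For stops 28 to 1000 days before first dose (1000 − 28 + 1 = 973 dates), 0 of 973 are concomitant. This follows directly from the definition.

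**Day missing.** The stop is imputed to month end, so it becomes concomitant only if stop and first dose share a calendar month. With a 28-day gap, first dose must fall on day 29, 30 or 31. In 2023 there are 11, 11 and 7 such dates:

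- 28 days: 11 + 11 + 7 = 29 of 365 first-dose dates
- 29 days: 11 + 7 = 18
- 30 days: 7
- 31 or 60 days: 0

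**Day and month missing.** The drug becomes concomitant when the recorded year is the year of first dose.

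**Wholly missing.** If the drug started before first dose and has stopped, it always becomes concomitant.

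**Illustration of dilution.** Let s be the true exposed share and q the share of exposed participants whose stop date is imputed to on or after first dose. Assume ORR 45% in the truly naive and 25% in the exposed. Both lie within the 20-45% range of protocol Table 19, but that table says nothing about brentuximab. Assume no on-study use.

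Labelled naive ORR = [(1 − s) × 0.45 + s(1 − q) × 0.25] / [(1 − s) + s(1 − q)]

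For s = 0.3, q = 0.1: (0.315 + 0.0675) / 0.97 = 39.4%. For s = 0.7, q = 0.1: (0.135 + 0.1575) / 0.93 = 31.5%.

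| s | q | Labelled naive ORR | Contrast with 25% (true: 20 points) | Labelled exposed per 100 (s × q) |
|---|---|---|---|---|
| 0.3 | 0.1 | 39.4% | 14.4 | 3 |
| 0.3 | 0.2 | 39.9% | 14.9 | 6 |
| 0.5 | 0.1 | 35.5% | 10.5 | 5 |
| 0.5 | 0.2 | 36.1% | 11.1 | 10 |
| 0.7 | 0.1 | 31.5% | 6.5 | 7 |
| 0.7 | 0.2 | 32.0% | 7.0 | 14 |

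With q = 0 and no on-study use, the exposed group is empty.

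**The case against.** The strongest reply is that SAP 4.2.2.6 names a record, not the derived class. SAP 4.1.8.1 sets its definitions for the medication summaries, and nothing says the subgroup must keep only rows classed as concomitant. Section 4.1.8 sorts medication into prior, concomitant and post-treatment, and 4.1.8.2 lists all three, so one file may hold everything. Prior anti-cancer therapy is coded in the same drug dictionary. The eCRF is not shown, so a single medication form cannot be ruled out.

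That possibility stands, but nothing in the documents says the concomitant record holds prior cHL therapy. SAP 4.2.7.2 lists concomitant-medication dates and alternative anticancer treatment dates as separate eCRF items, which leans the other way without settling it. On the single-file reading the rule still has no time limit, so brentuximab given after sabestomig would count as exposure. One can answer that naive and exposed ordinarily refer to history before treatment, but the SAP does not say so.

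The limits on size also stand. The 0 of 973 result is true by definition. The day-missing route operates only at gaps of 28 to 30 days. Every driver of the ORR illustration is assumed. The analysis is optional, no formal hypotheses are tested, and an empty exposed group would be noticed in a population with at least two prior lines.

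**Conclusion.** The concern holds. Followed as written, SAP 4.2.2.6 places previously treated participants with complete stop dates in the naive group, and the exposed group then depends mainly on date imputation or on-study use. If the record means all medication, the rule lacks a cut at first dose. Both readings need a different rule.

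The number affected cannot be computed. The 31.5-39.9% labelled naive ORR and the 6.5-14.9 point contrast show the direction and possible scale under the stated assumptions; they are not estimates for this trial. The consequence is confined to an optional, descriptive subgroup. It should be corrected, because it is a stated derivation rule that gives the wrong groups.

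**What to change.** In SAP 4.2.2.6 and 4.2.3.5, define exposed as any brentuximab vedotin in the coded prior anti-cancer therapy for cHL (the data summarized in SAP 4.1.7.2) with a start date before the first dose of sabestomig, and naive as all others. State that concomitant and post-treatment medication is not used.

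The cost is one sentence in each of two sections and one programming source. The data are already collected and coded, and nothing changes for sites or participants.
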